Ramucirumab (anti-VEGFR2) combined with the antitubulin agent paclitaxel leads to improved efficacy as compared to paclitaxel single agent as second-line therapy for the treatment of GC. The combination of ramucirumab plus paclitaxel was approved for second-line treatment of GC by the US FDA in November 2014, based on results from the Phase 3 RAINBOW study (2). This study evaluated paclitaxel (80 mg/m² IV on Days 1, 8, and 15 of a 28 day cycle) with or without ramucirumab (8 mg/kg IV infusion on Days 1 and 15 of a 28 day cycle) in subjects with metastatic gastric cancer refractory or progressive after first-line platinum and fluoropyrimidine therapy. Median OS was significantly improved for the combination (9.6 months) compared to paclitaxel alone (7.4 months), with a HR 0.807 (p=0.017). Median PFS was 4.4 months with the combination and 2.9 months with monotherapy, with a HR of 0.635 (p <0.0001) favoring the combination. Adverse events of Grade ≥3 occurring in more than 5% of participants were more frequent with combination treatment as compared to paclitaxel alone; incidences appeared to be elevated with the combination as compared to paclitaxel monotherapy for neutropenia (41% compared to 19%), leukopenia (17% compared to 7%), hypertension (14% compared to 2%), fatigue (12% compared to 5%), anemia (9% compared to 10%), and abdominal pain (6% compared to 3%).

Synergy of the activity of tusamitamab ravtansine (containing the cytotoxic antitubulin agent DM4) in combination with ramucirumab may lead to improved efficacy in the treatment of GC patients with a high unmet need; furthermore, this combination may have a better safety profile as compared to the combination of paclitaxel with ramucirumab. Nonclinical evaluations of the combination of tusamitamab ravtansine with a VEGFR2 antagonist were conducted in mice with GC PDX to evaluate substitution of paclitaxel with tusamitamab ravtansine in combination with ramucirumab. The results of these evaluations support clinical investigation of tusamitamab ravtansine in combination with ramucirumab: more extensive and sustained regression observed in evaluations of tusamitamab ravtansine in combination with the VEGFR2 antagonist as compared with paclitaxel in combination with anti-VEGF2 agent in GC PDX. Additionally, the observed safety profile for the tusamitamab ravtansine and anti-VEGFR2 combination in PDX

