Any patient who has had 1 tusamitamab ravtansine dose reduction or 2 ramucirumab dose reductions and who experiences an event that would cause an additional dose reduction must be discontinued from tusamitamab ravtansine/ramucirumab.

If 1 of the 2 drugs (tusamitamab ravtansine or ramucirumab) is prematurely permanently discontinued, the other drug can be continued until disease progression.

Retreatment of a patient requiring a dose delay of more than 1 month will need to be justified by an individual case risk-benefit assessment.

6.5.1 Retreatment criteria: Part 1 and Part 2

All participants entered into the study will be treated at Day 1. A participant may receive additional study interventions if he/she meets retreatment criteria as determined by the Investigator and agrees to be retreated.

At Day 1, the participant must meet all of the following criteria to be eligible for retreatment:

- Neutrophil count $\geq 1.5 \times 10^9/L$.
- Platelets $\geq 100 \times 10^9/L$.
- Total bilirubin $\leq 1.5 \times ULN$.
- AST, ALT $\leq 2.5 \times ULN$ or $\leq 5 \times ULN$ in case of documented liver metastasis.
- No IMP-related toxicity Grade >1 (except for alopecia) or baseline severity.

- Urine protein:
 - <2+ on dipstick or urinalysis for C1D1
 - ≤2+ on dipstick or urinalysis for subsequent infusions
- OR
- <2 g on 24 hour urine collection.
- Hypertension is controlled. Every attempt should be made to control blood pressure (<150 mmHg systolic and <90 mmHg diastolic).
 - Wound healing: any wound is fully healed.

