8.2.7.6 Hypertension

An increased incidence of severe hypertension (CTCAE Grade 3) has been reported in patients receiving ramucirumab as compared with placebo. In most cases, hypertension was controlled using standard antihypertensive treatment. Preexisting hypertension should be controlled before starting ramucirumab treatment. Monitoring of blood pressure is required during ramucirumab therapy. Every attempt should be made to control blood pressure to systolic <140 mmHg and diastolic <90 mmHg prior to starting treatment with ramucirumab. Routine clinical and laboratory monitoring is required in patients who again develop hypertension or experience a deterioration in previous hypertension.

Withhold ramucirumab for severe hypertension until medically controlled. Permanently discontinue ramucirumab for medically significant hypertension that cannot be controlled with antihypertensive therapy or in patients with hypertensive crisis or hypertensive encephalopathy.

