Neutrophil count decreased (continued)	Grade 4 >7 days <500/mm ³ ; <0.5 × 10 ⁹ /L	Delay the cycle until absolute neutrophil count >1500/mm ³ . 1st episode administer next cycle with ramucirumab at the same dose and administer growth factors 2nd episode: administer ramucirumab at the same dose 3rd episode: definitive discontinuation of IMPs	Delay the cycle until absolute neutrophil count >1500/mm ³ . 1 st episode administer tusamitamab ravtansine next cycle at the same dose and administer growth factors 2 nd episode: administer tusamitamab ravtansine at reduced dose 3 rd episode: definitive discontinuation	Follow ASCO guidelines on G-CSF usage and antibiotherapy (13). Repeat test every 3 days.
Febrile neutropenia	Grade 3 Absolute neutrophil count <1000/mm ³ with a single temperature of >38.3°C (101°F) or a sustained temperature of ≥38°C (100.4°F) for more than 1 hour	Delay cycle until absolute neutrophil count >1500/mm ³ . 1st episode administer next cycle at the same dose and administer G-CSF 2nd episode: administer ramucirumab at reduce dose 3rd episode: definitive discontinuation	Delay cycle until absolute neutrophil count >1500/mm ³ . 1 st episode administer next cycle at the same dose and administer G-CSF 2 nd episode: administer tusamitamab ravtansine at reduce dose 3 rd episode: definitive discontinuation	To ensure relative dose intensity, G-CSF is recommended as secondary prophylaxis in all patients with Grade 3 febrile neutropenia ASCO guideline is recommended for supportive treatment if there are no defined clinical standards (13).
	Grade 4 Life-threatening consequences	Administration changes to be decided at the Investigator's discretion per product label	Administration changes to be decided at the Investigator's discretion. 1 st episode: administer next cycle at reduced dose and administer G-CSF 2 nd episode: definitive discontinuation	
Hypertension	Grade 3 Severe hypertension	Withhold ramucirumab until controlled with medical management, and restart at same dose	Administer tusamitamab ravtansine the same day as ramucirumab	
	Grade 4 Severe hypertension that cannot be controlled with antihypertensive therapy	Definitively discontinue ramucirumab	Administer tusamitamab ravtansine as planned	

Event	Symptoms severity (Nadir) (NCI CTCAE v5)	Management of IMP dosing (ramucirumab)	Management of IMP dosing (tusamitamab ravtansine)	Supportive care guidelines

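### Appendix 6 omits two of the ramucirumab stopping triggers for hypertension in Section 8.2.7.6, and directs tusamitamab ravtansine where the retreatment criteria of Section 6.5.1 bar it

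*Protocol*

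**What the plan says.** Protocol Section 6.5 sends sites to Appendix 6 (Section 10.6) for cycle delays and dose changes. Appendix 6 has two hypertension rows.

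- **Grade 3**, labelled only as severe hypertension. Ramucirumab: "Withhold ramucirumab until controlled with medical management, and restart at same dose". Tusamitamab ravtansine: "Administer tusamitamab ravtansine the same day as ramucirumab".
- **Grade 4**, described as "Severe hypertension that cannot be controlled with antihypertensive therapy". Ramucirumab: "Definitively discontinue ramucirumab". Tusamitamab ravtansine: "Administer tusamitamab ravtansine as planned".

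Section 8.2.7.6 also withholds ramucirumab for severe hypertension until it is controlled. Its stopping rule is wider than the Grade 4 row: "Permanently discontinue ramucirumab for medically significant hypertension that cannot be controlled with antihypertensive therapy or in patients with hypertensive crisis or hypertensive encephalopathy".

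Section 6.5.1 lists the criteria for receiving additional study interventions on Day 1. All must be met, and one begins "Hypertension is controlled. Every attempt should be made to control blood pressure", with targets below 150 mmHg systolic and 90 mmHg diastolic. The list does not separate the two drugs and does not say what applies once one of them has been stopped permanently.

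**The concern.** There are two separate inconsistencies.

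**Ramucirumab.** Section 8.2.7.6 has three triggers for a permanent stop, and the Appendix 6 stopping row prints one. A hypertensive crisis or encephalopathy that responds to treatment is a permanent stop under Section 8.2.7.6. It does not fit the printed Grade 4 description, so a site working from the table could read it into the Grade 3 row and restart.

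**Tusamitamab ravtansine.** For hypertension that cannot be controlled, Appendix 6 lets the infusion go ahead. Section 6.5.1 makes control of hypertension a condition for any further study intervention. One text directs the infusion that the other bars.

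Hypertension is a named ramucirumab risk in this protocol, so patient safety is at stake first. The instruction followed also decides whether either drug continues. That feeds the exposure summaries and the counts of partial and full permanent discontinuation (SAP Sections 3.6.1, 3.6.2 and 5.2).

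**Working it through.** The check is mainly a side-by-side reading.

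| Situation | Section 8.2.7.6 | Appendix 6 | Section 6.5.1 | Consistent? |
|---|---|---|---|---|
| Severe hypertension, no crisis, later controlled | Withhold ramucirumab until controlled | Grade 3 row: the same, then unchanged dose; tusamitamab ravtansine given with it | Waits for control | Yes |
| Crisis or encephalopathy, later controlled: ramucirumab | Permanent stop | Not named in either row; Grade 3 on row wording, stop if graded 4 | Hypertension criterion met once controlled | No single instruction |
| Cannot be controlled: ramucirumab | Permanent stop | Permanent stop | Not eligible | Yes |
| Cannot be controlled: tusamitamab ravtansine | Silent | As planned | Not eligible | No |

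**Is the omission deliberate house style?** It does not look so. For proteinuria, Appendix 6 repeats the whole ramucirumab stopping rule of Section 8.2.7.7, including nephrotic syndrome. The ramucirumab stops for hemorrhage and arterial thromboembolic events also match Sections 8.2.7.8 and 8.2.7.9. The hypertension rule is the one cut short.

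**Does any text settle precedence?** Four were checked.

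- Section 6.5 says to follow the most conservative adjustment, but for a participant with several adverse events, not for two rules on one event.
- Section 6.5 falls back on the ramucirumab label only for events not listed in Appendix 6. Hypertension is listed.
- Section 8.2.7 refers to Appendix 6 and to the prescribing information, and calls its own content a reminder. It does not claim to override the table.
- Section 6.5 allows one drug to continue after the other is stopped. It does not waive the retreatment criteria.

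**Is the second mismatch confined to hypertension?** No. The first two proteinuria rows of Appendix 6 (first occurrence at 2 g per 24 hours or more; recurrence above 2 g) also give tusamitamab ravtansine as planned. Section 6.5.1 has a urine-protein criterion for later infusions: dipstick at most 2+, or less than 2 g in 24 hours. A participant above both limits is directed by one text and barred by the other. Section 6.5.1 also excludes IMP-related toxicity above Grade 1 or baseline severity, and ramucirumab is an IMP. Uncontrolled Grade 4 hypertension attributed to it would therefore fail that criterion too.

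**Size.** The only rate in the protocol is 14% Grade 3 or higher hypertension with ramucirumab plus paclitaxel, against 2% with paclitaxel alone (Section 2.1). The SAP expects 32 to 38 treated participants (Section 1.1).

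- Expected to enter either hypertension row, if that rate carries over: 0.14 × 32 = 4.5 to 0.14 × 38 = 5.3. Most of these would be in the first line of the table, where nothing conflicts.
- The share that are crises, encephalopathies or uncontrollable is not given. Assume 5% to 20%: 0.05 × 4.5 = 0.2 to 0.20 × 5.3 = 1.1 participants.
- Chance of at least one among 38: 1 − (1 − 0.14 × 0.05)^38 = 23% to 1 − (1 − 0.14 × 0.20)^38 = 66%.

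The last two lines rest on the assumed share and illustrate scale only. Proteinuria cases are not counted.

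**The case against.** **On ramucirumab.** Appendix 6 nowhere says to restart after a crisis or encephalopathy. Its rows are graded under CTCAE v5, and if such an event is Grade 4 on that scale, the row leads to the same stop as Section 8.2.7.6. The two texts can also be read as a general rule and a specific exception, and Section 6.5 lets the investigator discontinue for any event judged to warrant it. This stands in part. The documents do not reproduce the CTCAE definitions for hypertension, so the outcome depends on grading that cannot be checked here. Whatever the grade, the printed description still leaves out two listed triggers, and no text states the exception.

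**On tusamitamab ravtansine.** The instruction to proceed as planned may mean only that hypertension calls for no change to this drug, with Section 6.5.1 still gating each infusion. That reading is possible. But the row is defined by hypertension that cannot be controlled, so while that persists the gate would stay shut and the instruction would have no effect. The objection is right that the underlying gap is the scope of Section 6.5.1 by drug, as the proteinuria rows show.

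**Stronger readings that a reader might infer.**

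- That one participant meets both conflicts. The first needs hypertension that is later controlled, the second hypertension that cannot be.
- That Grade 3 hypertension in general is handled inconsistently. All three texts wait for control.
- That about 5 of 38 participants would receive opposing instructions. That figure counts everyone with Grade 3 or higher hypertension, and Section 8.2.7.6 says most cases were controlled with standard treatment.
- That the primary analysis is undermined. Response is assessed regardless of discontinuing study intervention (Protocol Section 9.3.2.2, SAP Section 3.2.2.1), so the estimand stays defined.

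**Conclusion.** Two inconsistencies stand, each on its own. Appendix 6 omits hypertensive crisis and encephalopathy from the ramucirumab stopping row, leaving room to read a controlled case into the restart row. It also directs tusamitamab ravtansine in uncontrolled hypertension, where Section 6.5.1 bars further study intervention; the first two proteinuria rows share this scope problem.

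The number affected cannot be derived from the documents and is probably about one participant or none. That rests on the 14% rate carrying over from the paclitaxel combination and on an assumed share of 5% to 20%. The first inconsistency also depends on how a site grades the event. The reason to correct the text is that the instructions concern a permanent stop and continuation of the investigational drug, not the expected count. No view is taken on which clinical rule is right.

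**What to change.** 1. Reconcile the hypertension rows of Appendix 6 with Section 8.2.7.6, so that uncontrollable hypertension, hypertensive crisis and hypertensive encephalopathy each appear with one stated action for each drug.
2. Reconcile Section 6.5.1 with Appendix 6 by stating which retreatment criteria gate which drug, including after ramucirumab has been permanently stopped. Cover the hypertension, urine-protein and general IMP-toxicity criteria together, since changing the hypertension criterion alone would leave the same gap elsewhere.
3. State which text governs if Appendix 6 and Section 8.2.7 differ.

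The clinical choice in each case is the sponsor's. The cost is protocol wording in a few table cells and one list of criteria, with no added visits, tests or analyses.

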10.8 APPENDIX 8: COUNTRY-SPECIFIC REQUIREMENTS

Serology for HBsAg, HCV, or HIV will be performed at screening only if required at the country level.

10.9 APPENDIX 9: CONTINGENCY MEASURES FOR A REGIONAL OR NATIONAL EMERGENCY THAT IS DECLARED BY A GOVERNMENTAL AGENCY

Continuation of the study in the event of a regional or national emergency declared by a governmental agency:

A regional or national emergency declared by a governmental agency (eg, public health emergency, natural disaster, pandemic, and terrorist attack) may prevent access to the clinical trial site.

Contingency procedures are suggested below for an emergency that prevents access to the study site, to ensure the safety of the participants, to consider continuity of the clinical study conduct, protect trial integrity, and assist in maintaining compliance with GCP in Conduct of Clinical Trials Guidance. Sponsor agreement **MUST** be obtained prior to the implementation of these procedures for the duration of the emergency.

During the emergency, if the site will be unable to adequately follow protocol mandated procedures, alternative treatment outside the clinical trial should be proposed, and prescreening/screening/enrollment/administration of study intervention may be temporarily delayed/halted.

Attempts should be made to perform all assessments in accordance with the approved protocol to the extent possible. In case this is not possible due to a temporary disruption caused by an emergency, focus should be given to assessments necessary to ensure the safety of participants and those important to preserving the main scientific value of the study.

Contingencies implemented due to emergency will be documented.

10.9.1 Remote prescreening process

If there is no other way to conduct prescreening procedures during a regional or national emergency declared by a governmental agency (eg, due to a COVID-19 pandemic), the site may consider implementing a remote prescreening ICF process compliant with country/site requirements for only those participants who have sufficient archival samples.

The process should be compliant with accepted principals of patients' rights and global, national, and local regulatory requirements. Required protection of personal data (including security of e-mail interactions) and confidentiality of study data should be ensured.

If remote prescreening is planned to be implemented at site:

- The Investigator/delegate should contact each participant to inquire regarding the participant's willingness to participate in the prescreening process.
- If participant agrees to pre-screening, the Investigator/delegate should send the pre-screening ICF via e-mail to the participant's personal e-mail address (as allowed by local regulation) or by postal mail. The Investigator/delegate should provide an overview of the study (eg, tusamitamab ravtansine mechanism of action; design of the study in terms of treatment groups, visits, and pre-screening procedures; and rationale for assessment of CEACAM5 expression). The Investigator/delegate should respond to any question raised by a participant, and this correspondence should be documented in detail in the participant's source file.
- If a participant agrees to participate in the pre-screening phase, the participant should print out, sign, and date 2 copies of the ICF. A scan of a signed ICF should be sent via secured e-mail (if available), and 1 of the signed original ICFs to be filed in the Investigator Study File should be sent via postal mail.
- The Investigator/delegate should review each received signed ICF (or a printout of an electronically submitted, scanned copy), sign and date it, and archive it in the Investigator Study File. It is mandatory for the Investigator to ensure the collection of the original signed ICF sent by mail; the signed original should be attached to any previously filed signed printout of an electronically submitted signed ICF. After properly documenting this consent process, the site may proceed to prepare and send the slides for CEACAM5 assessment.

10.9.2 Screening procedures

The Investigator/site should assess the site's capacity to conduct study procedures throughout the study for each participant before starting any screening procedure. If the site cannot guarantee an accurate follow-up in the context of the trial, alternative treatment outside the clinical trial should be proposed. This assessment, per the Investigator's medical judgement and depending on the country/site status, should be communicated to the participant. The participant should satisfy all eligibility criteria before enrolling to the study; and no protocol waiver is acceptable. Remote signature of main study ICF is not acceptable in any circumstance.

10.9.3 Study intervention

During a regional or national emergency declared by a governmental agency, all contingency plans should be implemented to ensure compliance to study treatment, based on a case-by-case benefit-risk assessment. Administration (or, in case of temporary interruption, reinitiation) of the IMP can occur only once the Investigator has determined, according to his/her best judgement, that the contribution of the IMP(s) to the occurrence of the epidemic event (eg, COVID-19) was unlikely.

Any further safety measure (eg, interim laboratory assessment such as neutrophil count monitoring; regular contact with site staff) to follow the safety of patients during the regional or national emergency period can be considered.

10.9.4 Study procedures

All efforts should be made to ensure that measurements of key parameters for efficacy endpoints can be performed at the site. If the Investigator is unable to guarantee that the protocol-required efficacy assessments can be conducted, no participant should be screened until the site confirms its capacity to perform the assessments.

As part of a site's contingency plan, a back-up site should be identified in advance in the case that the site delegated to perform the radiological tumor assessment is prevented from performing the assessment by a regional or national emergency situation (eg, COVID-19 outbreak). The Investigator should ensure that the back-up site conducts the RECIST assessment in same manner as that used for baseline tumor assessments.

In the case that the primary tumor assessment site is incapacitated, ongoing patients would then be referred to the back-up site for tumor assessment. The Investigator/delegate should ensure the information on baseline assessment methods is shared with the back-up site's radiologist to ensure same method is followed for scans.

Depending on site status, if needed, Cycle 1 and Cycle 2 weekly safety laboratory assessment (hematology [hemoglobin, hematocrit, RBC, WBC with differential, and platelet counts] and liver function tests [AST, ALT, total and conjugated bilirubin, ALP]) can be arranged to be performed either at a laboratory certified to perform these tests that is close to the patient's home, or via sampling at the patient's home.

10.9.5 Informed consent process

For a regional or national emergency declared by a governmental agency, contingency procedures may be implemented for the duration of the emergency. The participant or legally authorized representative should be informed verbally prior to initiating any change that is to be implemented for the duration of the emergency (eg, study visit delays, use of back-up sites for safety laboratory or tumor assessment).

